5.1. Analysis Specifications

5.2. Level of Significance

All statistical testing will be performed using a 2-sided test at the 10% level of significance, unless otherwise noted. Confidence intervals will be presented as 2-sided 90% confidence intervals.

Testing of Secondary Endpoints

The secondary endpoints are to be tested sequentially at the nominal 0.10 significance level (2-sided). The order of these endpoints is as follows:

1. ORR
2. Rate of subjects who proceed to stem cell transplantation
3. Duration of Response
4. OS
5. Tumor volume reduction rate
6. Time to Response

A secondary hypothesis will be tested if and only if the primary hypothesis is rejected along with all the secondary hypotheses that precede it.

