1.4. Sample Size Justification

Since Part 1 is to confirm that the pharmacokinetics in pediatric subjects is consistent with adults, no formal power calculations to pre-determine sample size were performed. The required number of subjects in Part 1 is based on pharmacokinetics results and clinical judgment.

In Part 2, approximately 72 subjects will be randomized. The sample size calculation for the randomized part (Part 2) is based on the assumption of 100% improvement (hazard ratio = 0.5) in median EFS in subjects receiving ibrutinib plus CIT (RICE or RVICI) compared with CIT (RICE or RVICI) (10 months versus 5 months). Utilizing a 2:1 randomization, this study will enroll approximately 72 subjects (approximately 48 subjects treated with ibrutinib [and RICE or RVICI background therapy]) during Part 2. Based on a total of 60 events for the 2 treatment groups, this study will have at least 80% power, given a 1-sided alpha of 0.05. An accrual rate of 1.44 subjects per month will result in a study duration of approximately 4.2 years.

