Overall Response Rate in Part 2	Primary	IRC assessed ORR chi-square test, Logistic regression model	ITT subjects with measurable disease at baseline
	Sensitivity	Investigator assessed ORR chi-square test, Logistic regression model	
	Subgroup	Logistic regression model	
Tumor Volume Reduction Rate		Analysis of variance (t-test) for percent decrease in the sum of the products of the lesion diameters at Day 14	ITT subjects with measurable disease at baseline
Time to Response		Non-stratified log-rank test, as the time interval from randomization to response for those subjects who respond as	ITT subjects who responded

Table 3: Summary of Efficacy Analyses to be Performed

Endpoint	Analysis	Analysis Method	Population
		assessed by IRC.	
Duration of Response		Non-stratified log-rank test, as the time interval from date of initial documentation of a response to the date of first documented evidence of progressive disease (PD) or death as assessed by IRC.	ITT subjects who responded
Rate of Subjects Who Proceed to Stem Cell Transplantation		Chi-square test for percent of subjects who proceed to stem cell transportation, Logistic regression model.	ITT
Other			
Subsequent Therapy		Descriptive summary Non-stratified log-rank test for the effect of subsequent antilymphoma therapy or a conditioning regimen for stem cell transplantation on overall survival, will be performed, as appropriate.	ITT subjects
Risk factors		Non-stratified Cox proportional hazards model using covariates to analyze the effect on EFS and survival will be performed, as appropriate.	ITT

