5.5.5. Time to Response

Time to response for subjects with either CR (including CR_b and CR_u) or PR as assessed by IRC is defined as the interval between the date of randomization and the date of initial documentation

of a response. Descriptive summary for time to response will be provided for each treatment group

Duration of Response

Duration of response for subjects achieving either CR (including CR_b and CR_u) or PR is defined as the interval between date of initial documentation of a response to the date of first documented evidence of progressive disease (PD) or death as assessed by IRC. The distribution for duration of response and median survival time with its 90% confidence interval will be estimated using the Kaplan-Meier product-limit method.

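### A responder-only comparison of duration of response must be significant before the all-randomized overall survival test can be made

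*SAP*

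**What the plan says.** SAP section 5.2 tests the secondary endpoints one after another at a nominal 2-sided 0.10. The order is ORR, transplant rate, DoR, OS, tumor volume reduction, time to response. The rule is: "A secondary hypothesis will be tested if and only if the primary hypothesis is rejected along with all the secondary hypotheses that precede it".

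SAP Table 3 gives the DoR analysis as "Non-stratified log-rank test, as the time interval from date of initial documentation of a response to the date of first documented evidence" of progression or death. Time to response also gets a non-stratified log-rank test. The population for both is "ITT subjects who responded".

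SAP section 5.5.5 names no test for either endpoint. For time to response it says "Descriptive summary for time to response will be provided for each treatment group"; for DoR it gives a Kaplan-Meier estimate and a 90% confidence interval. Protocol section 11.3.2 says that these endpoints will be summarized and sets no testing order.

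OS is compared by log-rank in all randomized Part 2 subjects (SAP section 5.5.1 and Table 3).

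**The concern.** Whether a subject responds is an outcome of treatment. Once the analysis is restricted to responders, randomization no longer makes the arms comparable. A drug that turns some non-responders into short-lived responders lengthens the list of responders and shortens their average duration. It can then look no better, or worse, on DoR although no patient has been harmed.

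As a descriptive summary this does little damage. As the third link of a fixed sequence it decides whether OS, which randomization does protect, may be formally tested. The sequence also makes the problem worse, because DoR is tested only after ORR is significant and so after the two responder groups have been selected at visibly different rates.

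**Working it through.** **Inputs from the documents.** About 72 subjects randomized 2:1 (48 and 24), 60 EFS events, EFS hazard ratio 0.5, 1-sided alpha 0.05 (SAP section 1.4); secondary tests at 2-sided 0.10 (SAP section 5.2); ORR 60% with RICE (protocol section 1.4). Everything else below is assumed, because the documents give no power, event count or expected effect for DoR, time to response or OS.

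**1. The plan's own figure.** Schoenfeld: power = Φ(√(d·p(1−p))·|ln HR| − 1.645), where d is the number of events and p the allocation fraction. With d = 60, p = 2/3 and HR 0.5: √(60 × 2/9) = 3.651; 3.651 × 0.693 = 2.531; 2.531 − 1.645 = 0.886; Φ = 81.2%. This agrees with "this study will have at least 80% power".

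**2. Same formula, responders only.** At 60% ORR in both arms there are 0.6 × 24 = 14.4 and 0.6 × 48 = 28.8 responders, 43.2 in total. A 2-sided 0.10 test has 5% in the favorable direction.

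| Share of responders with a DoR event | Events | Power, HR 0.5 | Power, HR 0.7 |
|---|---|---|---|
| 100% | 43.2 | 69% | 30% |
| 75% | 32.4 | 58-59% | 25% |
| 50% | 21.6 | 45% | 19% |

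A rough anchor: lack of CR or PR after 3 cycles is itself an EFS event, so 0.4 × 72 ≈ 29 non-responders would supply about 29 of the 60 EFS events and leave about 31 among responders. Then √(31 × 2/9) × 0.693 − 1.645 = 0.174, which is 57% power at HR 0.5.

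**3. What it takes to reach the DoR test.** If 14 of 24 controls respond (58%), 37 of 48 on ibrutinib (77%) gives a chi-square z of 1.65, just past the threshold of 1.645; 36 of 48 gives 1.45. With a true ORR of 60% in both arms, an exact calculation gives ORR significant in favor of ibrutinib in about 6% of trials. At 60% against 80% it is about 57%. So DoR is normally tested only when the observed response rates are well apart.

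**4. Selection, by arithmetic.** Suppose controls have 60% ORR and a median DoR of 12 months. Ibrutinib has the same 60% with the same durations plus 15% extra responders with a median of 4 months. Its responders are then 60/75 = 80% long and 20% short. At t = 9.5 months, 0.8 × 2^(−9.5/12) + 0.2 × 2^(−9.5/4) = 0.462 + 0.039 ≈ 0.50. The median DoR is about 9.5 months against 12, and no patient is worse off.

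**5. Selection, by simulation of the test.** Assumed: ORR 60% against 80%, median 10 months in those who would respond on either arm, follow-up uniform over 6-36 months, 20,000 runs.

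| Median DoR of extra responders | Ibrutinib significantly worse | Ibrutinib significantly better |
|---|---|---|
| 10 months (no selection) | 4% | 6% |
| 5 months | 10% | 2.5% |
| 2.5 months | 15% | 1% |

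**6. Effect on OS.** The whole chain was simulated (6,000 runs per row) with assumed response rates, transplant rates, median control DoR of 10 months and median post-event survival of 4 months.

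| ORR | Transplant rate | DoR HR | P(OS significant), as planned | P(OS significant), DoR removed | Gain |
|---|---|---|---|---|---|
| 60% vs 80% | 30% vs 50% | 0.5 | 0.210 | 0.322 | 11 points |
| 60% vs 80% | 30% vs 50% | 0.7 | 0.107 | 0.246 | 14 points |
| 60% vs 80% | 30% vs 50% | 1.0 | 0.024 | 0.120 | 10 points |
| 60% vs 70% | 30% vs 40% | 0.5 | 0.046 | 0.076 | 3 points |

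In the third row any OS benefit comes only from more patients responding, and the DoR test all but closes the route to it.

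**The case against.** Fixed-sequence testing is a valid way to control multiplicity, and the order of endpoints is the sponsor's choice. EFS already counts non-responders as events in the ITT population and must be significant before any secondary test. ORR and transplant rate stand ahead of DoR too, and in many scenarios the chain stops there. OS will be reported with its log-rank test, hazard ratio and interval whatever happens; only the formal claim is gated. Time to response is last and gates nothing. SAP section 5.3.1 makes the log-rank test the default for time-to-event variables, so the silence of section 5.5.5 on a DoR test is not a contradiction in itself. The short-duration responders in the illustrations have no basis in the documents. Protocol section 11.9.1 reports that the futility boundary was reached at 31 EFS events.

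All of this stands, and it limits the size of the point. It does not justify the gate: choosing an order is a matter of preference, but making a randomized OS test depend on a comparison that randomization does not protect is a design fault.

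A reader might infer that DoR alone would block OS at least half the time even with a large DoR effect. The documents do not support that. It needs an event count near the low end of the table in step 2, whereas the 60-event design points to about 31 events and blocking somewhat below half at HR 0.5. The equal-ORR case behind that calculation also rarely gets past the ORR test.

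**Conclusion.** The point holds as a fault in the testing hierarchy. It does not touch the primary analysis, and it is not a failure of type I error control. DoR is a weak gate: about 45-69% power at HR 0.5 and 19-30% at HR 0.7, before selection. Selection can push it in the wrong direction just when ORR has improved. Removing it is worth about 3 to 14 percentage points in the chance of a formal OS result, under assumed response rates, transplant rates, durations and follow-up. These figures show direction and rough size only.

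In practice the sequence opens only if EFS is rejected, which is unlikely after the futility result, although the stopping rule is non-binding. What remains live is the wording: for time to response, section 5.5.5 is descriptive while section 5.2 and Table 3 call for a test; for DoR, section 5.5.5 leaves unstated a test that OS depends on. As written, it is unclear whether the study report should carry p-values for these endpoints.

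**What to change.** In SAP section 5.2, delete DoR and time to response from the sequence, so that the order becomes ORR, transplant rate, OS, Day-14 tumor volume reduction. In Table 3, delete the log-rank tests for the two endpoints. Report both descriptively by arm: a summary for time to response and Kaplan-Meier estimates for DoR, as section 5.5.5 already provides. State there that no between-arm test is planned, since the default in section 5.3.1 would otherwise bring one back. If a comparison of response duration is wanted, use one that keeps all randomized subjects, such as time in response with non-responders counted as zero.

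The cost is SAP wording only, with no new data. What is given up is a confirmatory p-value for two responder-only endpoints.

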5.3. Data Handling Rules

Unless specified otherwise, imputation rules for missing and partial data are described in Section 2.7.

5.3.1. General Analysis Considerations

Descriptive statistics and subject listings will be used to summarize the data. For continuous variables, the number of observations, means, standard deviations, medians, and ranges will be used. For discrete variables, frequency will be provided. For time-to-event variables, Kaplan-Meier estimates will be provided.

Comparisons between the 2 treatment arms in Part 2 will be performed as follows: for the continuous variables representing change from baseline to a particular postbaseline timepoint, analysis of variance will be used. For discrete variables, Chi-square test will be used. For time-to-event variables, non-stratified log-rank test and non-stratified Cox proportion hazard model will be used unless specified otherwise. All tests will be conducted at 2-sided test at the 10% level of significance and 90% confidence intervals will be provided, unless otherwise stated.

Unless otherwise specified, disease progression and disease response will be based on assessments from an IRC, according to principles adapted from the International Pediatric NHL Response Criteria (Sandlund 2015).² Disease response will be evaluated by radiological imaging, physical examination, or other procedures as necessary, including but not limited to review of hematology, clinical chemistry, and lumbar puncture results. Criteria for response categories, as well as the process and convention of the IRC are detailed in a separate IRC charter.

5.4. Primary Efficacy Endpoint

5.4.1. Event-free Survival (EFS) Based on IRC

The primary efficacy endpoint is EFS in Part 2, which is defined as the time interval from randomization to death, disease progression, or lack of CR or PR after 3 cycles of treatment, based on blinded independent event review by the IRC, whichever occurs first. The process and conventions of the IRC will be detailed in a separate IRC charter. The analysis of the primary endpoint (EFS) will be based on the ITT population.

5.4.2. Primary Analysis Methods for EFS

Subjects who continue to respond after 3 cycles of treatment, are progression free and alive will be censored at the date of last disease assessment. Subjects with no baseline or any post-baseline disease assessment will be censored at the date of randomization.

The analysis of the primary endpoint (EFS) will be based on the ITT population. For the primary efficacy analysis, EFS will be compared between treatment groups using a non-stratified log-rank test. The Kaplan-Meier method will be used to estimate the distribution functions of EFS for each treatment group. The number of events, subjects censored, the estimate of medians, and 90% confidence interval for the medians will be presented. The plot of EFS using the Kaplan-Meier method will be presented. The estimate of the hazard ratio between the 2 treatment groups and its associated 90% confidence interval will be computed based on the non-stratified Cox proportional hazards model.

5.4.3. Sensitivity Analysis of EFS

Sensitivity analysis will be performed for EFS as follows:

1. Use of subsequent antilymphoma therapy or a conditioning regimen for cell transplantation prior to documented PD or death.

Two alternative censoring rules will be performed for subjects who start subsequent therapy prior to first documentation of disease progression or death due to any cause:

- a. Subjects will be considered to have had an EFS event at the initiation of subsequent therapy.
- b. Subjects will be censored at the last disease assessment showing no evidence of PD before the use of subsequent antineoplastic therapy.

2. Disease assessment follow up: Subjects will be censored at the last disease assessment if they progress, die or have not responded after missing ≥ 2 planned disease assessment visits.
3. EFS based on investigator assessments: For this sensitivity analysis, the same censoring rules and analysis methods used for primary analysis of IRC reported EFS will be used. The concordance rate between the IRC-determined EFS and investigator-determined EFS will be evaluated. The number and percentage of the following cases determined by investigator and by IRC will be cross-tabulated:
 - a. PD events and censored cases
 - b. CR or PR after 3 cycles of treatment

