8.4. Subsequent Antilymphoma Therapies

Administration of subsequent antilymphoma therapy is not allowed until:

- Confirmed residual disease after completion of at least 3 cycles of study treatment, or
- PD (or relapse after CR) any time during treatment as established according to the criteria described in Section [9.2.5.2](#), Response Categories.

Note that the medical monitor must be notified of the subject's suspected PD and all imaging, bone marrow, and cerebrospinal fluid (CSF) disease analyses are required to be centrally reviewed before a subject is removed from study therapy. Subjects who have not progressed while on therapy and who receive subsequent therapy for NHL will continue to be followed until PD. For any subsequent antilymphoma therapy, the start date, end date, and best response should be documented in the appropriate section of the electronic CRF.

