5. EFFICACY

Analysis of efficacy endpoints will be conducted on the ITT population. [Table 3](#) summarizes the efficacy endpoints and analysis methods to be performed.

Table 3: Summary of Efficacy Analyses to be Performed

Endpoint	Analysis	Analysis Method	Population
Primary			
Event-free Survival (EFS) as assessed by IRC	Primary	Non-stratified log-rank test, non-stratified Cox regression model, all PD and death considered as events regardless of subsequent antilymphoma therapy or a conditioning regimen for stem cell transplantation. EFS is defined as the time interval from randomization to death, disease progression, or lack of CR or PR after 3 cycles of treatment.	ITT
	Sensitivity	
 1) Alternative censoring rule 1: subjects who received subsequent antilymphoma therapy or a conditioning regimen for cell transplantation are considered to have had an EFS event at the initiation of subsequent therapy 2) Alternative censoring rule 2: subjects who received subsequent antilymphoma therapy or a conditioning regimen for cell transplantation are censored at the last disease assessment showing no evidence of PD before the use of subsequent therapy 3) Alternative censoring rule 3: subjects will be censored at the last disease assessment if they progress, die or have not responded after missing ≥ 2 planned disease assessment visits. 4) Investigator assessed EFS by non-stratified log-rank test and non-stratified Cox regression model; concordance rate between the IRC-determined EFS and investigator-determined EFS 	ITT
	Subgroup	Non-stratified Cox regression model within each subgroup	ITT
Secondary			
Long-term survival (EFS) at 2 and 3 years		IRC assessed chi-square test for 2 and 3 year EFS rate.	ITT
Overall Survival	Primary	Non-stratified log-rank test, non-stratified Cox regression model, as the time interval from enrollment (Part 1) or randomization (Part 2) to all deaths considered as events regardless of subsequent antilymphoma therapy or a conditioning regimen for stem cell transplantation.	ITT
	Sensitivity	Censored at subsequent antilymphoma therapy or a conditioning regimen for stem cell transplantation.	
Overall Response in Part 1	Subgroup	Non-stratified Cox regression model within each subgroup Listing of IRC and investigator assessments for those subjects who respond.	ITT Enrolled subjects

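### SAP 5.4.3(1) leaves non-response out of the trigger for its subsequent-therapy rules, so rule (b) as written censors subjects who have already had an EFS event

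*SAP*

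**What the plan says.** - SAP 5.4.1 defines EFS as the "time interval from randomization to death, disease progression, or lack of CR or PR after 3 cycles of treatment", whichever comes first, by blinded IRC review. Protocol 11.3.1 agrees.
- SAP 5.4.3(1) sets two alternative rules "for subjects who start subsequent therapy prior to first documentation of disease progression or death due to any cause". Rule (a): "Subjects will be considered to have had an EFS event at the initiation of subsequent therapy". Rule (b): "Subjects will be censored at the last disease assessment showing no evidence of PD before the use of subsequent antineoplastic therapy".
- SAP 5.4.3(2), the missed-visits rule, names non-response alongside progression and death.
- SAP Table 3 restates both rules for any subject who received subsequent therapy. Under its second rule such subjects "are censored at the last disease assessment showing no evidence of PD before the use of subsequent therapy". The condition that therapy must precede PD or death is missing there.
- Protocol 8.4 opens subsequent therapy in two situations: PD or relapse, and "Confirmed residual disease after completion of at least 3 cycles of study treatment". Protocol 9.1.4 repeats the second.
- Protocol 9.1.3 asks for the End-of-Treatment visit before any subsequent therapy starts. It also lets a subject with confirmed CR after 2 cycles go to transplant.
- Protocol Table 9 keeps minor response (MR) and no response (NR) separate from PD.

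**The concern.** The endpoint has three event types and the trigger for the sensitivity rules has two. The missing one, non-response, is closely tied to a reason for which the protocol allows new therapy without PD. A subject assessed as MR or NR at End of Treatment has had an EFS event. If new therapy follows before PD or death, that subject still meets the trigger.

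Under rule (b) the event then becomes a censored observation. Those censored are treatment failures, so the censoring is informative. The result would be read as a robustness check on the primary analysis, although for these subjects it drops one component of the endpoint.

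**Working it through.** **Following one subject through the text.**
1. End of Treatment after Cycle 3: IRC response MR or NR, no PD. Under SAP 5.4.1 this is an EFS event.
2. New therapy starts for residual disease, as Protocol 8.4 permits, after the End-of-Treatment visit (Protocol 9.1.3).
3. There has been no PD or death, so the trigger in SAP 5.4.3(1) is met.
4. Rule (b): the last assessment without PD is normally the End-of-Treatment assessment itself. The subject is censored at the point where the primary analysis has an event.
5. Rule (a): the subject remains an event, but at the later therapy start date.

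A subject in PR with residual disease, or in CR going to transplant, has no EFS event at step 1. For these subjects both rules do what they are meant to do.

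**The plan's own figure.** The documents give no figure for any sensitivity analysis. The stated power of at least 80% (SAP 1.4) belongs to the primary test. It reproduces: Φ(ln 2 × √(60 × 2/9) − 1.645) = Φ(0.886) = 81.2%. It is not in question here.

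**Size under rule (b).** Let q be the share of randomized subjects who are MR/NR and start therapy before PD or death. Let p be the share with any other EFS event by End of Treatment. Assume no other censoring up to then.
- Events turned into censored observations: 72 × q. For q = 10%, 7.2; for q = 20%, 14.4.
- Kaplan-Meier EFS just after End of Treatment: 1 − p − q in the primary analysis, 1 − p under rule (b). The difference is q, whatever p is. With p = 20% for display, q = 10% gives 70% against 80%, and q = 20% gives 60% against 80%.

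The value of q is an assumption. The nearest guide is the RICE study described in Protocol 1.2. There 40% (8/20) failed therapy, with median survival 2.5 months from entry. Three 28-day cycles last 84 days, about 2.76 months, so about half of such failures would have died by then. That leaves at most about 20% of subjects alive without response, before PD among them is removed.

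Enrollment stopped after the interim review at 31 EFS events (Protocol 11.9.1). The number randomized is not given. At the 46 subjects projected for the interim in SAP Table 2, q = 10% is 4.6 subjects.

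**Direction of the hazard ratio.** Illustrative simulation with 2,000 trials per row:
- 48 versus 24 subjects, exponential times to PD or death with medians 10 and 5 months;
- follow-up uniform from 3 to 40 months;
- the stated share of those still event-free at 2.76 months is non-responding, and all of them start therapy, one month later under rule (a);
- hazard ratio from the one-step log-rank estimate.

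| Non-response, control / ibrutinib | Primary | Rule (a) | Rule (b) |
|---|---|---|---|
| 20% / 20% | 0.507 | 0.497 | 0.435 |
| 20% / 10% | 0.424 | 0.426 | 0.425 |
| 30% / 15% | 0.420 | 0.424 | 0.429 |
| 40% / 20% | 0.411 | 0.418 | 0.433 |

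Rule (b) makes the effect look larger when non-response is equal by arm. It makes the effect look smaller when control has twice as much at the higher rates. Rule (a) moves the estimate by at most 0.010.

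**The case against.** The best reply is that EFS is defined by whichever event comes first, so a subject with a non-response event is finished and the rules concern only subjects without an event. Item 2 of the same section names non-response where it is to be overridden, so its absence from item 1 could mean that such events stand. A programmer might well work that way.

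That reading is reasonable, but the SAP does not state it. Item 1 is an explicit alternative to the primary event and censoring scheme. Its trigger includes these subjects, its censoring date is tied to absence of PD rather than absence of an event, and it has no exemption. Two programmers could derive different event counts from the same text.

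Several limits do stand:
- Only rule (b) censors. A reader might infer that both rules turn events into censored observations; rule (a) keeps them as events.
- A reader might infer that everyone starting new therapy early is mishandled. Subjects in PR, or in CR going to transplant, are not.
- A share of 30% might be tempting as an upper case. It would need three quarters of failures (0.30/0.40) to be alive without PD at End of Treatment, which fits poorly with the 2.5-month median in Protocol 1.2.
- A reader might compute a loss of power from the lower event count. That holds the hazard ratio at 0.5 while removing an endpoint component that changes it. No power figure is supported, and the plan claims none for this analysis.
- Table 3 is a summary and 5.4.3 carries the fuller condition, so the wider wording in Table 3 is a matter of alignment.

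**Conclusion.** The concern holds for rule (b) as written. MR/NR subjects who start new therapy after Cycle 3 and before PD or death are changed from events to censored observations, normally at the assessment that established the event. Rule (a) has a smaller fault from the same trigger.

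Each 10% of 72 subjects in this position costs about 7 events and adds about 10 points to EFS just after End of Treatment. This assumes that all of them start therapy before PD or death and that there is no other censoring up to then. The actual share is not in the documents. The Kaplan-Meier curve of an affected arm is pushed upward; the hazard ratio can move either way.

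A reader might infer that the primary result or the futility finding is affected. The documents do not support that: the primary analysis in SAP 5.4.1 and 5.4.2 uses the three-part definition and does not use these rules. The point concerns the meaning of one pre-specified sensitivity analysis and should be corrected before that analysis is run.

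**What to change.** In SAP 5.4.3(1) and the matching Table 3 rows, apply both rules only to subjects who start subsequent therapy before their first EFS event of any type: death, IRC-assessed PD, or IRC-assessed lack of CR or PR after 3 cycles. State that a non-response event remains an event under both rules, at the date used in the primary analysis.

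SAP 5.4.1 and 5.4.2 give no date for that event, so the SAP should add one, for example the date of the IRC End-of-Treatment assessment.

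The cost is a sentence in 5.4.3(1), matching wording in Table 3, and a line on the event date. No new data are needed.
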